1.0 Rationale

Chronic obstructive pulmonary disease, also known as COPD, is a debilitating disease that affects a growing percentage of the Canadian population (Public Health Agency of Canada, 2007). COPD is characterized by chronic and progressive airflow limitations causing shortness of breath, chronic cough, and sputum production (Public Health Agency of Canada, 2008). COPD includes chronic bronchitis and emphysema, as well as other similar respiratory illnesses and is primarily caused by smoking cigarettes, though other causes do exist (Public Health Agency of Canada, 2008). The airflow limitation can affect oxygen transfer in the lungs, increasing the effort required to perform activities of daily living such as: walking, climbing stairs, and gardening (Annegarn et al., 2012). To date, COPD is not fully reversible, but various treatments (e.g., exercise, medications) are available to help manage the disease. Approximately 4% of the Canadian population report being diagnosed with COPD; however, 13% of Canadians were found to have a lung function score indicative of COPD (Statistics Canada, 2013). It is believed that COPD will become the third leading cause of death by 2030, and according to the last World Health Organization estimate in 2004, 64 million people are currently living with COPD (World Health Organization, 2015).

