2.0 Purpose

The overall goal of this study is to identify the priorities of individuals living with COPD in terms of their activities and participation, as well as their research priorities and health care concerns. To achieve this overall goal, the study is divided into three phases (see Figure 1). The purpose of the *first phase* is to develop and pilot test a questionnaire created for individuals living with COPD to assess their activities, participation, and health care and COPD-related research priorities. The Activities, Healthcare and Research Priorities Questionnaire (AHRPQ) was developed based on past research, then verified by a panel of COPD and participation experts to gather their opinions and recommendations. The AHRPQ was then examined by adults with COPD in focus groups, where they provided feedback on the content and readability of the questionnaire. Five focus group participants were also invited to complete the full survey online as an initial pilot test.

The purpose of the *second phase* of the study is to compare across diagnosed COPD stages and disease severity the extent to which adults with COPD participate in the listed activities and identify their primary research and health-care related priorities. The AHRPQ will be administered at three sites across Montreal where clinical data for each participant will be available. This phase will also help establish the reliability of the questionnaire.

In the *third phase*, the purpose is to administer the questionnaire to a pan-Canadian sample to identify the activities that individuals living with COPD participate in, the barriers that limit their participation in these activities, the activities that are of most importance for this population, and their health concerns and research priorities. We will also be examining the relationship between participation and quality of life related outcomes. The questionnaire will be distributed to a larger population of individuals living with COPD who self-report their COPD diagnostic/severity.

This amendment is to add the protocol for the *second phase* of the study. We presented the overall goal in order to contextualize the current application.

[figure not shown]

Figure 1: The three phases of the study, broken down into each step of the phases. The identified phase (Phase 2) is the following protocol amendment.

References

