Before the questionnaire package has been completed, participants will be prompted to provide their full name, date of birth and street name to gather their medical chart information. Their street name will be asked to ensure that the correct individual in the system has been identified. Participants will be compensated \$50 for their time and any inconveniences experienced by answering the questionnaire. If they choose to stop taking part in the study, they will not be compensated for the study.

The questionnaire package contains the AHRPQ (APPENDIX D) and additional questionnaires (APPENDIX E) to gather information on other aspects of their lives. Specifically, these additional questionnaires are: the Godin Leisure Time Physical Activity Questionnaire, the Medical Research Council Questionnaire on Breathlessness, the Charlson Comorbidities Index, the COPD Assessment Test, the Satisfaction with Life Questionnaire, the St. George's Respiratory Questionnaire, the Canadian Cohort Obstructive Lung Disease CanCOLD questionnaire, and demographic information (i.e., age and gender).

The information gathered from the medical charts includes participants: COPD status/severity (GOLD stage, % predicted FEV₁, FEV₁/FVC); comorbidities (confirming the self-report responses from the Charlson Comorbidities Index questionnaire (Appendix E; e.g., diabetes, cardiovascular disease, mental health, asthma)); Smoking cessation (confirming the self-reported smoking cessation answered by the participant in the Medical Research Council

questionnaire on breathlessness (Appendix E); and gather other health related information such as height and weight.

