Project Title: Patients with COPD preferences, activities, and participation survey

NCT Number: NCT02970422

Principal Investigators:

[name].

Department of Kinesiology & Physical Education, Faculty of Education, McGill University.

[contact] [name]

Email: [contact]

[name].

Department of Kinesiology & Physical Education, Faculty of Education, McGill University.

[contact] [name]

Email: [contact]

Statistical Analysis

To assess individuals' airflow obstruction (disease severity), quartiles of FEV_{1%predicted} were used. Quartiles of FEV_{1%predicted} were used because we could not confirm that individuals' spirometry was done post-bronchodilator. Thus, we were unable to use the Global Initiative for Obstructive Lung Disease (GOLD) COPD staging system (23). Nevertheless, all individuals self-reported a physician diagnosis of COPD and were recruited through their healthcare providers who confirmed the diagnosis. Individuals were divided into quartiles based on their FEV_{1%} predicted, with quartiles 1, 2, 3 and 4 representing those with mild (Q1), moderate (Q2), severe (Q3) and very severe (Q4) airflow obstruction, respectively. Only individuals with a FEV₁/FVC ratio <0.70 were included in the quartiles of airflow obstruction.

Individuals' breathlessness burden and exacerbation risk groups were based on their mMRC breathlessness scores and 12-month exacerbation history (20): group A (low breathlessness + low exacerbation risk), mMRC ≤1 with ≤1 exacerbation that did not lead to

hospital admission; group B (high breathlessness + low exacerbation risk), mMRC ≥ 2 with ≤ 1 exacerbation not leading to hospital admission; group C (low breathlessness + high exacerbation risk), mMRC ≤ 1 with ≥ 2 exacerbations or ≥ 1 exacerbation that led to hospital admission; and group D (high breathlessness + high exacerbation risk), mMRC score ≥ 2 and ≥ 2 exacerbations or >1 exacerbation that led to hospital admission.

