Descriptive statistics were used to report individuals' daily and social participation and provide a picture of how respondents participated in each activity. The distribution of the scores for each activity was assessed based on quartiles of airflow obstruction, breathlessness burden and exacerbation risk, sex, age, and PR participation status. Using IBM SPSS Statistical software (v.23), chi-square analysis, with standardized residuals post-hoc analyses, were performed on the participation items individually to determine if the observed value differed from the statistically expected value for quartiles of airflow obstruction, breathlessness burden and exacerbation risk, sex, age, and PR participation status. To examine the barriers and facilitators to participation, descriptive statistics were used to identify the most common barrier/facilitator. A repeated measures analysis of variance (ANOVA) was used to determine if there was a significant difference between the barrier/facilitator that was selected the most often compared to all other barriers/facilitators.

Descriptive statistics were used to report individuals' healthcare and research priorities. The distribution of the scores for each activity was assessed based on quartiles of airflow obstruction and exacerbation burden and exacerbation risk. Using IBM SPSS Statistical software (v.23), chi-square analysis, with standardized residuals post-hoc analyses, were performed to determine if the observed number of responders for each healthcare and research topics differed

from the statistically expected value for airflow obstruction and exacerbation burden and exacerbation risk. Additionally, non-parametric tests were conducted to determine if there were any between group differences for the healthcare and research topics and airflow obstruction and exacerbation burden and exacerbation risk groups. A Kruskal-Wallis non-parametric test was conducted due to the non-normality of the data, as the mean for both healthcare and research topics was skewed. Individuals giving 10% of their time/funding was the most common response for each of the healthcare or research topics. Post-hoc analyses with Bonferroni corrections were also conducted.

For the secondary outcomes, one-way ANOVAs were used to determine mean group differences. However, for both FEV1% predicted and physical activity levels, a Kruskal-Wallis non-parametric test was conducted as the data was non-normal.

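### The comparison of participation by PR status is a crude chi-square with no adjusted result beside it, so a significant item may reflect differences in severity, age or sex

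*SAP*

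**What the plan says.** The SAP (Statistical Analysis, participation items) states that "chi-square analysis, with standardized residuals post-hoc analyses, were performed on the participation items individually". The observed value is compared with the "expected value for quartiles of airflow obstruction, breathlessness burden and exacerbation risk, sex, age, and PR participation status". These five groupings are listed in parallel, and no covariate or stratification is named for any of them.

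The other methods in the SAP are repeated measures ANOVA for barriers and facilitators, chi-square and Kruskal-Wallis tests for healthcare and research topics, and one-way ANOVA or Kruskal-Wallis tests for secondary outcomes. None of them adjusts the comparison by PR status.

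The protocol (2.0 Purpose) says of the Phase 2 sites that "clinical data for each participant will be available". Section 3.0 lists "COPD status/severity (GOLD stage, % predicted FEV₁, FEV₁/FVC" among the chart data. It lists "the Medical Research Council Questionnaire on Breathlessness" and demographic information in the questionnaire package. The SAP itself uses mMRC score and 12-month exacerbation history to form groups A to D.

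**The concern.** The Rationale (protocol 1.0) describes airflow limitation as "increasing the effort required to perform activities of daily living such as" walking and climbing stairs. The SAP also tests the same items against airflow and breathlessness. The study therefore treats severity as a plausible influence on participation.

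PR status is observed, not assigned. Nothing in the documents balances severity, age or sex between PR and non-PR participants, or says that their balance was examined. Testing severity in a separate chi-square does not remove it from the PR chi-square.

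Of the five groupings, PR is the only treatment. A significant item could be read as saying something about PR when it only describes who attends it. The protocol (2.1 and 5.0) plans to send results to health care professionals and the COPD community, so the reading matters.

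**Working it through.** **No figure to reproduce.** The documents give no sample size, significance level, number in PR, severity by PR status or item response rates. Everything below is an assumption, made to show how the size of the problem depends on the inputs.

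**Set-up.** There are two severity strata and no PR effect within either.
- *a*, *b*: share with severe disease among PR and non-PR participants
- *s*, *m*: proportion limited on an item among severe and less severe people
- *n*: number per group; two-sided level 0.05

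**Formulas.**
- Crude rates: PR = a·s + (1−a)·m; non-PR = b·s + (1−b)·m
- Gap = (a−b)(s−m)
- Noncentrality of the crude chi-square (1 df): λ = gap² / [2·p̄(1−p̄)/n], where p̄ is the mean of the two crude rates
- Rejection rate = P(noncentral χ² with 1 df and λ > 3.841)

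**One case in full** (a = 0.60, b = 0.40, s = 0.60, m = 0.30, n = 100).
- PR: 0.60×0.60 + 0.40×0.30 = 0.48
- Non-PR: 0.40×0.60 + 0.60×0.30 = 0.42
- Gap: 0.20×0.30 = 0.06
- λ = 0.0036 / (2×0.45×0.55/100) = 0.0036/0.00495 = 0.727
- Rejection rate: 13.7%

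**Range.**

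| Severe share, PR / non-PR | Limited, severe / less severe | Crude rates | Gap (points) | Crude test rejects, n = 50 / 100 / 150 per group |
|---|---|---|---|---|
| 50% / 50% | 60% / 30% | 45% v 45% | 0 | 5% / 5% / 5% |
| 60% / 40% | 50% / 30% | 42% v 38% | 4 | 7% / 9% / 11% |
| 60% / 40% | 60% / 30% | 48% v 42% | 6 | 9% / 14% / 18% |
| 70% / 40% | 60% / 30% | 51% v 42% | 9 | 15% / 25% / 35% |
| 70% / 30% | 70% / 30% | 58% v 42% | 16 | 36% / 62% / 79% |

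If non-PR participants are the more severe group, the gap changes sign. In simulation (20,000 replicates per scenario) a Cochran-Mantel-Haenszel test stratified by severity rejected in 4.7% to 5.2% of studies throughout. That result assumes that PR does not itself change the stratifying variable.

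**When that assumption fails.** Suppose PR lowers the share with mMRC ≥2 from 60% to 40%, and difficulty with an item is 50% at mMRC ≥2 and 20% below.
- Without PR: 0.60×0.50 + 0.40×0.20 = 0.38
- With PR: 0.40×0.50 + 0.60×0.20 = 0.32

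The overall PR difference is a real 6 points. Within each mMRC stratum it is zero, so an mMRC-stratified test would show nothing. The choice of adjustment variables therefore matters as much as the decision to adjust.

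**The case against.** The strongest reply is that the SAP claims no PR effect. The Phase 2 purpose (protocol 2.0) concerns COPD stage and severity, and PR is one of five groupings in a largely descriptive analysis. As a test of marginal association the crude chi-square is valid: if PR participants are more breathless and more limited, that association is real. This stands. The weakness lies in what can be concluded from the result, not in the test.

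A reader might infer that the PR comparison is in fact biased, or that its false-positive rate is known to be high. The documents support neither, because severity by PR status is not reported. The link between severity and participation may also be modest. The reference list gives the title of the work cited in the Rationale for daily activities, and it describes the association with clinical characteristics as weak. Only the title is visible, but it is a reason not to lean on the larger figures.

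A reader might also infer that the PR conclusion should rest on an mMRC-adjusted test. The documents do not support that. mMRC and 12-month exacerbation history are recorded at a single survey, and nothing places them before PR.

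Nor is severity certain to be complete for everyone. Questions may be skipped (protocol 4.0), and the SAP says that "Only individuals with a FEV₁/FVC ratio <0.70 were included in the quartiles of airflow obstruction". It also could not confirm that spirometry was post-bronchodilator. Adjustment for FEV1 may therefore leave some confounding in place.

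**Conclusion.** The point holds in a limited form. The PR comparison is crude, PR is not randomised, nothing else in the plan adjusts it, and the plan already provides for FEV1, age and sex. A significant item therefore cannot be separated from a difference in severity, age or sex.

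The size is unknown. On the assumed inputs the crude gap runs from 0 to 16 points, and rejection with no PR effect from 5% to 79%. The outcome depends on how far severity differs by PR status and how strongly it drives each item. The documents fix neither, and the direction is equally open.

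The point is confined to the participation items, since PR is not a grouping for the healthcare and research topics. It does not affect the comparisons across airflow or breathlessness groups.

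**What to change.** 1. Tabulate % predicted FEV1, mMRC, exacerbation history, age and sex by PR status, with the number missing for each.
2. Keep the crude chi-square for each item and label it unadjusted.
3. Beside it, report a logistic or ordinal regression of the item on PR status with continuous % predicted FEV1, age and sex, giving the adjusted odds ratio and its 95% interval. Continuous FEV1 is preferable because the quartiles are undefined at FEV1/FVC of 0.70 or above. State whether those people are kept in the model.
4. As a sensitivity analysis only, add mMRC and exacerbation history to the model, or use a Cochran-Mantel-Haenszel test stratified by them. State that both are measured at the survey and may lie on the PR pathway.
5. Word any PR result as an association.

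The cost is a little more analysis on data the plan already collects. People without a usable FEV1 drop out of the adjusted model, so crude and adjusted results may rest on different numbers. Both denominators should be given.

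### Groups A–D cross breathlessness with exacerbation risk but are tested only as one grouping, so the plan has no test or estimate of either factor adjusted for the other

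*SAP*

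**What the plan says.** The SAP (Statistical Analysis) states that the "breathlessness burden and exacerbation risk groups were based on their mMRC breathlessness scores and 12-month exacerbation history". The first three cells are "group A (low breathlessness + low exacerbation risk"), "group B (high breathlessness + low exacerbation risk") and "group C (low breathlessness + high exacerbation risk"). Group D is high on both. Breathlessness is cut at mMRC 1 or below against 2 or above.

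The high-risk limb is worded differently in the two high-risk groups. Group C has "≥ 2 exacerbations or ≥ 1 exacerbation that led to hospital admission" and group D has "≥ 2 exacerbations or >1 exacerbation that led to hospital admission".

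For participation, "chi-square analysis, with standardized residuals post-hoc analyses, were performed on the participation items individually", and the classification variables include A–D as one entry: "for quartiles of airflow obstruction, breathlessness burden and exacerbation risk, sex, age, and PR participation status". For healthcare and research topics, the SAP adds Kruskal-Wallis tests across groups and Bonferroni-corrected post-hoc analyses, without listing the contrasts. Secondary outcomes use one-way ANOVA, or Kruskal-Wallis for two of them, with the groups unnamed.

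The SAP never calls A–D a four-level factor. That reading follows from its defining four groups and no separate breathlessness or risk variable. In the topics paragraph the label of the grouping also changes, with exacerbation in place of breathlessness as the burden. I read this as the same A–D grouping.

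**The concern.** A significant four-group test says only that the groups are not all alike. It does not say whether participation varies with breathlessness at a given exacerbation risk, with exacerbation risk at a given breathlessness, or with both. Protocol section 1.0 gives breathlessness as its own example of a reason that may limit participation, so a reader will want that answer. The data needed for it are already collected to form the groups.

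Standardized residuals do not supply it. Each one compares a cell count with the count expected from the margins. None contrasts high with low breathlessness within a risk level. There is also a cost in power when only one factor matters, because the 3-df test spreads its sensitivity over every possible pattern of group differences.

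**Working it through.** The documents give no sample size, alpha, power, group sizes, item response levels or effect size, so there is no figure of theirs to reproduce. Every numerical input below is an assumption.

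**Step 1. One factor acting, balanced groups, binary item, alpha 0.05.** Power is the upper tail of a noncentral chi-square with noncentrality λ beyond the central critical value (3.84 on 1 df, 7.81 on 3 df).
- λ for 80% power is 7.85 on 1 df and 10.90 on 3 df. The ratio 10.90/7.85 = 1.39 is the sample-size inflation.
- At λ = 7.85 the 3-df test has 64.5% power.
- With 3, 4 or 5 response levels (k − 1 against 3(k − 1) df), the four-group test has 62%, 61% or 60% where the two-group test has 80%.

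**Step 2. Allow for testing two factors.** The 1-df test at alpha 0.05/2 = 0.025 and λ = 7.85 has 71.2% power, still above 64.5%.

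**Step 3. Both factors acting equally and additively, balanced groups.** The omnibus noncentrality is 2 × 7.85 = 15.70, giving 93% on 3 df. With two tests at 0.025, the chance of detecting at least one factor is 1 − (1 − 0.712)² = 92%. Detection is about equal, but only the two-factor analysis says which factor acts.

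**Step 4. Illustration: N = 200, item endorsed by 60% v 40% according to breathlessness only.** For the stratified 1-df test, λ = N × 0.20² × I / 0.25, where I = ab/(a+b) + cd/(c+d) and a to d are the group fractions.

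| Groups A/B/C/D | I | λ (1 df) | 1 df, 0.05 | 1 df, 0.025 | 3 df, 0.05 |
|---|---|---|---|---|---|
| 25/25/25/25% | 0.250 | 8.00 | 81% | 72% | 65% |
| 35/30/10/25% | 0.1615 + 0.0714 = 0.233 | 7.45 | 78% | 69% | 65% |

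Pairwise tests at 0.05/6 = 0.0083 that isolate breathlessness (A v B, C v D) have 26% each in balanced groups, and 36% and 13% in the unequal split. These are for a binary item and only indicate what pairwise tests on topic shares might do.

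**Step 5. Simulated item, groups of 60/70/16/54, endorsed by 65% v 45% according to breathlessness.** The four-group chi-square rejects in about 64% of runs, and a breathlessness test stratified by risk in about 77%. Some standardized residual, (O − E)/√E, exceeds 1.96 in only about 25%.

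**Step 6. Adding the interaction to the same model.** For a 30/35/8/27% split with the additive 1-df test at 80%, the 3-df test has 67%. With an interaction fitted, the breathlessness term has 71% if effect-coded and 66% if reference-coded. In balanced groups the reference-coded term has 51% against 64.5% for the 3-df test. The power advantage therefore belongs to the additive model.

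**Step 7. Is the cross complete as written?** Take a participant with mMRC 2 or above and a single exacerbation, which led to admission. Groups A and C are excluded by mMRC. Group B is excluded because the exacerbation led to admission. Group D is excluded because there are neither two exacerbations nor more than one with admission. This participant fits no group, whereas one with the same history and mMRC of 1 or below falls in group C.

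**The case against.** Four points are made against the concern.

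**The plan never set out to separate the factors.** Protocol section 2.0 aims to compare across COPD stages and disease severity, and A–D is a composite taken from a cited source. Comparing its four groups is a legitimate question, and the planned tests answer it. This stands as a reason to keep them.

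**A reader might infer that the plan cannot say which factor matters.** That goes too far. If the Bonferroni post-hoc analyses for the topics are all pairwise, A v B and C v D isolate breathlessness, and A v C and B v D isolate exacerbation risk. They would be weak, and the SAP does not list them, but weak is not impossible. For participation items no such contrasts are described.

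**A reader might infer that the four-group test always loses power.** It does not. The loss holds when one factor acts, and disappears when both act equally (Step 3). A fair comparison must also charge the two-factor analysis for its extra tests. Splitting alpha over two factors leaves 71% against 64.5% in balanced groups, and only 69% against 65% in the unequal split of Step 4. Splitting it over both factors and an interaction leaves 65.8%, so no real gain. The case for the addition rests mainly on attribution, with power as a secondary benefit.

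**The risk factor is not yet defined in one way.** This is correct and must be settled first. It affects the existing A–D tests equally, so it is not a reason to avoid the two-factor analysis.

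**Conclusion.** The concern holds in a limited form. A–D is a two-by-two classification carried into one-way tests, and no test or estimate of either factor adjusted for the other, or of their interaction, is described. This matters most for participation items.

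The size is roughly 64% power for the 3-df test where an additive factor test has 80%, or 71% after a two-test correction. That assumes alpha 0.05, balanced groups and one factor acting. The advantage narrows with unequal groups and can vanish or reverse if the interaction is fitted in the same model. When both factors act, nothing is lost in detection, only in attribution.

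Nothing here makes the planned tests invalid; they are incomplete for attributing a difference. Separately from any assumption, the definitions of groups C and D leave one type of participant unclassified.

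**What to change.** 1. Reconcile the high-risk wording of groups C and D so that every participant with complete data falls in exactly one group, and use one label for the grouping throughout the SAP.
2. Keep the A–D tests and descriptive display.
3. Add a supplementary analysis with high breathlessness and high exacerbation risk as two additive factors. Use logistic or ordinal logistic regression for participation items, and a rank-based two-factor or stratified test for topic shares. Report each factor's effect with a 95% interval, adjusted for the other.
4. Examine the interaction in a separate model, so that it does not dilute the main estimates.
5. Apply a multiplicity correction for the two factor tests.
6. List the contrasts in the Bonferroni post-hoc analyses.

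The SAP is written in the past tense, so the addition should be labelled supplementary. No new data are needed. The cost is one extra table and more tests per item. The interaction will be poorly estimated if one cell is small, and if the two factors truly interact the additive effects are less informative, which is why the check is reported beside them.

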2.1 Expected Outcomes

Patients living with COPD are not always provided with sufficient information to answer their questions concerning the disease and its impact on quality of life. The debilitating nature of COPD has a large impact on the daily, social and community activities performed by people living with COPD. By gathering information on the extent to which people with COPD want to participate in various activities and the barriers to their limit their participation, we will better understand the needs of this population. This information can then be disseminated to health care providers and health researchers. A second benefit of this study is understanding the specific health topics that are most important to people living with COPD. Because health care providers are the primary source of information for this population, prioritizing these health topics can greatly improve patient care. Lastly, identifying the patients' COPD research priorities can guide future research on the domains that are most important to this population. By improving our understanding of the specific activities and topics that are prioritized by people living with COPD, we can better inform future research and hopefully improve the care and management of COPD.

The results of the study will be disseminated through conference presentations and publications in peer-reviewed journals. A lay summary will be distributed to the COPD community (e.g., through the Quebec Lung Association) and related health care professionals once the results have been finalized.

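### Does the SAP need a named contrast and adjustment before it can say that the most-selected barrier or facilitator differs from all the others?

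*SAP*

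**What the plan says.** The SAP's Statistical Analysis section gives this question two sentences. First, "descriptive statistics were used to identify the most common barrier/facilitator". Second, a repeated measures ANOVA was used "to determine if there was a significant difference between the barrier/facilitator that was selected the most often compared to all other barriers/facilitators". Nothing more is said about this step.

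Other steps in the same section do have a named follow-up. The chi-square tests, "with standardized residuals post-hoc analyses, were performed on the participation items individually", have one. The next paragraph, on healthcare and research priorities, ends with "Post-hoc analyses with Bonferroni corrections were also conducted". That sentence comes straight after the Kruskal-Wallis text for those topics, and its position does not support extending it back to the ANOVA.

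The protocol has no statistical text on the point. Section 2.0 lists "the barriers that limit their participation in these activities" under the third phase, whereas this protocol adds the second. Section 2.1 includes barriers among the expected outputs of the study. Section 3.0 says "The questionnaire package contains the AHRPQ (APPENDIX D"; that appendix is not in the supplied text, so the response format of the barrier items is unknown here.

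**The concern.** The overall F of a repeated measures ANOVA tests whether all items are equally common. The SAP asks something narrower: whether one item stands apart from the rest. If two items share first place and the others are well below, F will be significant although neither leads.

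A contrast has its own difficulty, because the top item is chosen from the same data used to test it. Comparing it with the average of the others, or declaring any single difference from it, then has a false-positive rate above the nominal level. With no contrast, adjustment or rule named, a reader cannot tell from the SAP which test supports a statement that a given barrier is significantly the most common. At stake is whether a tie for first could be reported as a single leader.

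**Working it through.** The plan states no figure for this analysis, so there is nothing to reproduce. The inputs below are assumptions, because the documents give no sample size, item count, selection rates or significance level: k = 8 items, N = 100 to 200, two-sided 0.05, independent yes/no selections and paired t comparisons.

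**1. What F can show.** Take two items at 40% and six at 10%. The mean rate is (2 × 0.40 + 6 × 0.10)/8 = 0.175. The sum of squared deviations is 2 × 0.225² + 6 × 0.075² = 0.135. The mean within-item variance is (2 × 0.24 + 6 × 0.09)/8 = 0.1275. At N = 100 the between-item signal relative to error is (100 × 0.135/7)/0.1275 = 1.929/0.1275 = 15.1, against a critical F of about 2.02 on 7 and 693 degrees of freedom. F therefore rejects essentially always; in simulation it did so in 100% of runs.

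**2. Top item against the average of the others, same tie.** The difference is 0.40 − (0.40 + 0.60)/7 = 0.257. Its standard error at N = 100 is √[(0.24 + (0.24 + 0.54)/49)/100] = 0.0506, so t is about 5.1. This also rejects in 100% of simulated runs, with no true leader.

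**3. Top item against each other item, all required to be significant, same tie.** To be called leader, the observed top item must significantly exceed the item it is tied with. Either of the two can come out on top, each with probability 0.025 of doing so significantly, so the false-leader rate is at most 0.025 + 0.025 = 0.05. Simulation gave about 5% at N = 100 and at N = 200. Selecting the top item from the data does not break this bound, because the bound already counts both candidates.

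**4. All eight items equal (20% each).** Simulated rates of a positive claim:

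| Claim | Rate |
|---|---|
| Top item beats every other item | about 0.1% |
| Top item differs from the average of the others, unadjusted | about 12–15% |
| Top item differs from at least one other, unadjusted | about 50% |
| Top item differs from at least one other, read only after a significant F | about 5% |

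The 50% belongs to a claim of at least one difference. The SAP's question is whether the top item differs from all the others, and the first row answers that.

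**5. What the strict rule gives up.** For a true leader at 45% against a runner-up at 30% (six others at 10%), N = 100 gives a standard error of √[(0.2475 + 0.21)/100] = 0.0676, so z = 0.15/0.0676 = 2.22 and power is about 58–59%. At N = 200 it is about 88%. For 40% against 35%, simulated power is only 11–18% over the range of N.

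**The case for a change.** The strongest case for a change is that the SAP itself adds a significance claim to a descriptive ranking and leaves open what the claim rests on. The choice matters. With eight equal items the false-positive rate runs from about 0.1% to about 50%, depending on what is declared. Reading comparisons only after a significant F restores about 5% when all items are equal, but does nothing for tied leaders, where F always rejects. Extending the later Bonferroni sentence to this step would not settle it: for a claim of at least one difference, correcting over only the k − 1 comparisons with a data-selected top item still gave about 9–15% (5 to 10 items at 30%), against about 4% when correcting over all pairs. Section 2.1 of the protocol does name barriers among the things the study will report to providers and researchers.

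Part of this stands. The SAP does not say whether the comparison is with each other item or with their average, and under the second reading, or if F alone were used, a tie could pass as a lead. What does not stand is the step from an unstated procedure to a wrong one. No sentence makes F or the average carry the claim. The stated aim, one item against the rest, already points to follow-up comparisons, and the each-item reading needs no adjustment when all must be significant. The large error rates attach to a claim that the SAP does not make. Nothing in the documents suggests a near-tie, and the tied scenario produces its result by construction.

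**Conclusion.** No change to the plan follows. The SAP leaves out operational detail that an analyst would ordinarily supply: the ANOVA as the overall test, then the top item against each of the others. On that reading a false leader is named about 5% of the time or less, without adjustment, even though the top item is picked from the data. The bound at a two-way tie follows from the two-sided 0.05 level and does not depend on the assumed item count or rates; the other percentages do depend on the assumed 8 items, 100 to 200 respondents and selection rates, and are not trial figures.

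The remaining ambiguity, a tie reported as a lead, arises only under readings that the text does not adopt. It would affect a supporting result for which neither document states a hypothesis, a significance level or a decision. The descriptive ranking of barriers and facilitators is unaffected. Requiring a strict leader rule in the plan would also be a trade-off, since modest true leads would often go undeclared.
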